6.5 Period of follow-up

For Cohorts 1-3:

Per protocol Section 6.2.3, Week 4/Day 28 evaluations will serve as the study completion evaluations for participants who have maintained an HIV-1 RNA level of < 200 copies/mL by standard ultrasensitive assay at the Day 7 visit. Also, these evaluations will be the study completion evaluations for participants who did not experience a Grade \geq 3 AE or clinical event (per protocol Section 7.1).

Participants who experience a Grade \geq 3 AE or clinical event must return for a Week 8/Day 56 visit (per protocol Section 7.1.2).

Per protocol Section 6.2.4, participants with an HIV-1 RNA level of \geq 200 copies/ml at the Day 7 visit will be contacted immediately and asked to return as soon as possible (preferably within 72 hours) for a repeat HIV-1 RNA PCR. If the repeat HIV-1 RNA PCR level after Day 7 is \geq 200 copies/ml, the participant will complete both Week 4 /Day 28 and Week 8 /Day 56 visits.

For Cohort 4:

Per protocol Section 6.1, participants will be followed for 18 weeks after the 4th infusion. Note: infusions can be delayed per protocol.

6.6 Visit schedule and definition of "Day" and "Week" for analysis purposes

Days and Weeks on study will be based on the study treatment administration dates (i.e., will be " anchored" on the infusion timing) and will use the protocol-specified windows. The protocol schedule of events for Cohort 4 is provided in **Appendix 1**.

6.7 Validation of programs

All programs creating treatment codes, derived datasets, formats, and primary analysis programs will be validated in accordance with SOP PROG.10066 and PROG.10067 (or PROG.10083, as applicable). All user options files will be validated in accordance with SOP PROG.10071.

The primary analyses (safety and efficacy) will be additionally validated through independent coding.

7 ANALYSES

Analysis summaries will be presented for each dose cohort active arm, for the pooled dose cohort arms (if applicable), the pooled placebo arms (if applicable), and overall. Separate analyses may be performed by cohort in which summaries will be by active dose cohort, placebo arm and overall.

For SMC reports all summaries will be presented by randomized treatment, and overall, separately by dose cohort.

Lists will be indexed by the alternate participant identifier (**PUBLICID** variable), and visit week/date as needed.

7.1 Accrual

- a. Table: number (%) of participants enrolled by month/year
- b. Table: number (%) of participants enrolled by site

[STATUS dataset]

7.2 Eligibility Violations

- a. Table: violations of eligibility criteria by site (if any)
- b. List: details of exclusions from analyses (if any)

7.3 Participant Replacement

Table: reasons for replaced participants (if any), as described in protocol Section 9.4.

7.4 Baseline Characteristics

a. Table (demographic information):

- Age at randomization date (years): N, median, 25th and 75th percentiles, min, max; number (%) by category (18-34, 35-49, ≥50)
- Sex: number (%)
- Self-reported race/ethnicity: number (%)
- IV drug use: number (%) by category (never used, previously used, currently used)
- BMI (kg/m²): N, median, 25th and 75th percentiles, min, max
- Background ART regimen: number (%) by category (raltegravir, dolutegravir, efavirenz)

[STATUS dataset, PKW0348 form, ANSTAB table (for background regimen)]

b. Table (health status information):

- Time since first HIV-1 RNA below the detection limit: N, median, 25th and 75th percentiles, min, max and number (%) by category (1-3, 3-5, 5-10, 10-15, 15-20, 20+)
- History of VF on an ART regimen: number (%)
- Nadir CD4 count: N, median, 25th and 75th percentiles, min, max
- Screening CD4 count (cells/mm³): N, median, 25th and 75th percentiles, min, max
- Screening HIV-1 RNA level by SCA (copies/mL): N, median, 25th and 75th percentiles, min, max
- Screening negative HCV antibody: number (%) by category (Yes, No)
- Pre-entry ECG result: QTC interval (msec): N, median, 25th and 75th percentiles, min, max

[HXW182 form, HXW183 form, F1015 form, ANSTAB table, F0875 form]

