on days 1, 8, and 15 of a 28-day cycle, usually for multiple cycles. Following a 4-hour intravenous administration of RMD at 14 mg/m² on days 1, 8, and 15 of a 28-day cycle in patients with T-cell lymphomas, the terminal half-life (t1/2) was approximately 3 hours. No accumulation of RMD was observed after repeated dosing. Early clinical trials of RMD in CTCL patients revealed a potentially increased risk of QTc prolongation. As a result, the package insert for this drug indicates that it should not be given to a patient with a prolonged QTc. Side effects of RMD at the MTD include nausea, fatigue, vomiting, and anorexia. Common first cycle toxicities reported include bone marrow suppression and transient elevations of liver function tests [24-25, 32]. In clinical trials of RMD for T-cell lymphoma, bone marrow suppression has been associated with fatal and serious infections as well as reactivation of EBV and hepatitis B virus, RMD is predominantly metabolized by the cytochrome P450 enzyme CYP3A4. RMD is highly protein bound in plasma (92% to 94%) over the concentration range of 50 ng/mL to 1000 ng/mL with α 1-acid-glycoprotein (AAG) being the principal binding protein. Although there are no formal drug interaction studies for RMD, strong CYP3A4 inhibitors may increase plasma concentrations of RMD. RMD is also a substrate of the efflux transporter P-gp (ABSB1); hence drugs that inhibit P-gp may increase plasma concentrations of RMD. Finally, RMD competes with beta estradiol for binding to estrogen receptors, which inhibits their function (RMD Investigators Brochure v 10.0 May 2012).

HIV-infected	Fold increase	p value			
donor	over no drug control	vs. control			
1	4.8	0.03			
2	5.6	0.006			
3	14.0	0.0008			
4	3.0	0.0005			
5	5.9	0.02			
6	14.0	0.02			
7	5.2	0.00002			
8	2.8	0.01			
9	16.0	0.00003			
10	20.1	0.0003			
11	1.8	0.4			
12	5.8	0.005			
13	12.3	0.001			
	Avg = 8.6				
HIV-1 RNA levels were measured by Roche Taqman v2.0 at day 6 in culture supernatants of CD4+ memory T-cells from patients on suppressive ART. Intracellular HIV RNA was not measured.					

Table **2.2-1**: Induction of HIV-1 RNA *ex vivo*

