6.3.8 ECG

Resting ECG results, including heart rate and measured QTc interval, must be recorded per the SOE. For the ECG done during pre-entry, the QTc interval must be read by a cardiologist and signed off by the site investigator prior to the start of the RMD/placebo infusion and should ideally be taken from limb lead II.

For the ECGs that are performed at the completion of the RMD/placebo infusion (Hour 4) and 2 weeks later, the QTc interval must be read by a cardiologist but this reading may be done at a later time and QTc interval will be recorded. See section 7.1.5 for clinical management directions for participants with a prolonged QTc interval on study.

NOTE: Should ECGs be performed for any reason at visits after entry, the site is responsible for recording any change in QTc interval relative to the baseline value.

A program for calculating QTc by Fridericia's correction is available on the DMC website at www.fstrf.org.

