7.1.5 Cardiac Toxicity

Refer to the A5315 MOPS for the DAIDS Toxicity Table to grade QTc prolongation.

- Grade 1: Infusion should continue without interruption, at the discretion of the site investigator.
- Grade 2: Infusion should continue without interruption, at the discretion of the site investigator. A repeat ECG should be performed at the 7 and 14 days following the infusion.
- Grade 3 and 4: The infusion should be interrupted. If the Grade 3 QTc prolongation is considered to be most likely due to concomitant illness or medication, standard management, including discontinuation of the likely causative agent, should be undertaken. A repeat ECG should be performed 7 and 14 days after the infusion.

Several treatment-emergent changes in ECGs (including T-wave and STsegment changes) have been reported in clinical studies of RMD. The clinical significance of these changes is unknown. In this study, electrolytes and ECGs are monitored at Pre-Entry and then again after each infusion. The use of strong CYP3A4 inhibitors that may increase RMD concentrations is prohibited during the study. ECG changes observed in participants may be multifactorial. Clinicians should evaluate participants with ECG changes for other possible contributing factors and address any that are identified. Sites should contact the core team ([contact]) to help determine whether additional infusions should be cancelled.

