7.9 Safety data

7.9.1 List of events

List showing all the grade > 0 safety events for each study participant. The list will include the following:

- public ID
- treatment dispensation days
- core team assigned code (regarding the relatedness to study treatment)
- visit week
- onset day
- resolution day
- event description
- value and units (for laboratory results)
- grade
- site assigned code (regarding the relatedness to study treatment)

NOTE: This information corresponds to the ToxSum report prepared by the DMC, with the addition of the site assigned code. The site assigned code is derived from the TRAC table for events, except for those who originate from the EVW0206; the site assigned code for these events is derived from the EVW0206_UPDATE dataset

[TRAC table, EVW0206_UPDATE dataset]

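### QTc is recorded after every infusion as a potential romidepsin risk, but the SAP summarises it only at pre-entry and plans no estimate of post-infusion change by arm

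*SAP*

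**What the plan says.** Protocol 2.2 gives the reason for ECG monitoring: "Early clinical trials of RMD in CTCL patients revealed a potentially increased risk of QTc prolongation". Protocol 7.1.5 states that "electrolytes and ECGs are monitored at Pre-Entry and then again after each infusion".

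The schedules in Protocol 6.1 place an ECG at pre-entry, at Hour 4 of each infusion, and once more at Day 14 in Cohorts 1-3 or at Week 8 in Cohort 4 (R+2 weeks on the delayed Step 4 schedule). Protocol 6.3.8 requires a cardiologist to read the Hour 4 and two-week QTc; "this reading may be done at a later time and QTc interval will be recorded". For ECGs after entry, "the site is responsible for recording any change in QTc interval relative to the baseline value".

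In the SAP, QTc appears once, in 7.4 Baseline Characteristics: "Pre-entry ECG result: QTC interval (msec", with N, median, quartiles, minimum and maximum. SAP 7.9 (safety) consists of listings and the dose-escalation criteria; the broadest item is 7.9.1: "List showing all the grade > 0 safety events for each study participant".

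**The concern.** Safety and tolerability form the first primary objective, and the protocol treats the placebo arm as necessary for judging treatment-related toxicity. QTc is a continuous measurement, taken before and after dosing in both arms, on a risk that the protocol itself names. Protocol 7.1.5 adds that ECG changes have been reported with RMD, that their clinical significance is unknown, and that several factors may contribute to them. A comparison of change against randomised placebo is the analysis that addresses such uncertainty.

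Under the plan as written, a QTc value after dosing is seen only if it is graded. A general rise that stays below the grading limits would appear in no table, for any dose. By contrast, SAP 7.14.8-7.14.11 plan summary tables and rank tests for CD4 percentage, activation markers, annexin V/7-AAD and P-TEFb in Cohort 4.

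**Working it through.** The documents state no QTc sample size, SD or threshold for analysis, so there is no planned figure to reproduce. The check has three parts.

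**1. What is recorded, against what is reported**

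- Recorded: pre-entry QTc; Hour 4 QTc at each infusion; a later scheduled QTc; change from baseline (Protocol 6.1, 6.3.8). Protocol 6.3 requires evaluations to be entered on the CRF and keyed unless stated otherwise.
- SAP 7.4: pre-entry QTc only.
- SAP 7.9 to 7.15: no post-infusion QTc value, change, count or comparison of arms.
- SAP 5.1.1 and 5.1.2 (annual and dose-escalation SMC reports): these draw on the same SAP sections and add no QTc output.
- Protocol 9.2 and 9.6: no QTc outcome or analysis.
- Adverse-event route: Protocol 7.1.5 says "Refer to the A5315 MOPS for the DAIDS Toxicity Table to grade QTc prolongation". Graded prolongation can then appear in the listings of SAP 7.9.1, 7.9.3, 7.11.8 and 7.14.7, and in the by-arm summary of Grade 2 or higher events in Protocol 9.6. This route carries threshold crossings only.

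**2. How many readings**

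- At full enrollment: 45 × 2 + 15 × 5 = 165 scheduled post-infusion readings.
- Protocol 2.2 reports 15 participants in Cohort 1 and 14 in Cohort 2, and allows 12 to 15 in Cohort 3. The total is then (15 + 14 + 12) × 2 + 75 = 157, up to (15 + 14 + 15) × 2 + 75 = 163.

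**3. What precision the added analysis would have**

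Group sizes come from Protocol 9.4.2: 36 RMD and 9 pooled placebo in Cohorts 1-3, 12 RMD per dose, and 12 v 3 in Cohort 4. The SD of QTc change is assumed to be 15 ms, with a range of 10 to 20 ms. The 95% half-width, used as an approximation to that of a Hodges-Lehmann interval, is

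t(0.975, n1 + n2 − 2) × SD × √(1/n1 + 1/n2).

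- 36 v 9: 2.017 × 15 × 0.373 = 11.3 ms (7.5 to 15.0 over the SD range)
- 12 v 9: 2.093 × 15 × 0.441 = 13.8 ms (9.2 to 18.5)
- 12 v 3: 2.160 × 15 × 0.645 = 20.9 ms (13.9 to 27.9)

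The difference detectable with 80% power (two-sided 5%, noncentral t) at SD 15 ms is 16.0 ms for 36 v 9, 19.5 ms for 12 v 9 and 29.4 ms for 12 v 3. Smaller enrollment widens all of these intervals.

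**The case against.** The strongest reply is that the SAP follows the protocol. Protocol 9.2 defines safety as related Grade 3 or higher events, with Grade 2-4 events as a secondary outcome, and names no QTc outcome. Nothing promised has been dropped. This stands: the gap lies in both documents, and the SAP does not depart from the protocol.

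A second reply is that QTc is already watched. Prolongation is graded, sites contact the core team about ECG changes, the core safety team reviews individual data, and the SMC reviews all safety data after each cohort. This also stands, and a reader should not infer that QTc prolongation goes unmonitored. But these routes act on individual cases and graded events; none gives the distribution of change by arm. How large a rise they would miss cannot be calculated, because the grading limits are in the MOPS, which is not among the documents.

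A third reply is that the estimate would be too imprecise to help. At 36 v 9, a 10 ms shift would sit inside a half-width of about 11 ms, and pooling 0.5, 2 and 5 mg/m² may dilute a dose effect. This limits what the table can show and rules out reading it as evidence of no effect. It is a reason to print the interval, not to leave the data untabulated.

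**Conclusion.** The gap is confirmed. QTc is recorded after every infusion because of a named potential risk, and the SAP summarises the interval only at pre-entry. Graded events are the sole planned route for post-infusion values.

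A reader might infer that the trial is unable to estimate an effect on QTc. The documents do not support that: the values are recorded, placebo is randomised, and SAP section 1 allows the plan to be modified. The accurate statement is that no such estimate is planned. Nor is an effect established; Protocol 2.2 speaks only of a potentially increased risk.

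The point is worth acting on because the remedy is cheap, but the gain is modest. With an assumed SD of 15 ms, the half-width is about 11 ms for pooled Cohorts 1-3, 14 ms for one dose against pooled placebo and 21 ms for Cohort 4. These figures assume full enrollment, which Cohort 2 did not reach and Cohort 3 need not reach.

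**What to change.** Add one descriptive table to SAP 7.9:

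- **Content:** QTc and change from the pre-entry ECG at each scheduled post-infusion ECG, with N, median, quartiles, minimum and maximum. Add the number above 450 ms, labelled as the entry-exclusion value of Protocol 4.2.9 and 4.4.9 and not as an on-study safety limit.
- **Groups:** each dose arm and pooled placebo in Cohorts 1-3; RMD and placebo separately in Cohort 4.
- **Contrast:** the Hodges-Lehmann RMD-minus-placebo shift with 95% interval, for each dose as well as pooled. SAP 7.13.1 already uses this estimator. Present it as estimation, not as a test of no effect.
- **Baseline:** name the pre-entry ECG explicitly. The general rule in SAP 6.4 takes the last evaluation on or before Day 0, and the first Hour 4 ECG can fall on that day. In Cohort 4 the pre-entry ECG is 28 to 35 days before the first infusion, so emphasise the placebo-corrected change there.
- **Reports:** the final report and the annual SMC report. Inclusion in the dose-escalation report is optional, since SAP 5.1.2 abbreviates it to speed review.

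A matching line in Protocol 9.6 would keep the two documents aligned. The cost is the programming and validation of one table from data already collected. The downside is a wide interval, which the table should show openly.

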7.5 Study Status

a. Table:

- Number (%) of participants who completed the protocol
- Number (%) of participants who did not complete the protocol
 - Number (%) of participants off study due to death
 - Number (%) of participants off study prior to completion of protocol for reasons other than death
- b. List of lost-to follow-up participants (if any) with follow-up duration and reason off study
- c. List of deaths (if any) including study week of death and cause of death information

[STATUS dataset]

7.6 Treatment Status

For Cohorts 1-3:

a. Table:

- Number (%) of participants who completed RMD/placebo infusion
- Number (%) of participants who discontinued prematurely RMD/placebo infusion
- c. List: details (including reasons and % infused) for participants with incomplete treatment, if any

For Cohort 4:

a. Table:

- Number (%) of participants who completed all 4 RMD/placebo infusions
- Number (%) of participants who did not complete all 4 RMD/placebo infusions
 - Reasons why not all 4 RMD/placebo infusions were not completed

b. List: details (including reasons and % infused) for participants with incomplete treatment, if any

NOTE: For final analysis the duration of infusion (hours) will also be summarized (N, median, 25th and 75th percentiles, min, and max)

[TXW0279 form, STATUS dataset]

7.7 HIV-1 RNA level at day 7 after each infusion

a. Table: HIV-1 RNA level (copies/mL) at day 7 after each infusion: number (%) by category (<40 (G), <40 (J), 40-199, ≥200)

NOTE: The table will have a footnote listing all the HIV-1 RNA levels at day 7 that are ≥40 copies/mL

[RNALDMS dataset]

7.8 Data and stored sample completeness (interim analysis only)

Tables summarizing completeness of selected data and stored sample (using the CBAR macro %DAR):

- BLD/DPE/CEL/DMS or BLD/EDT/CEL/DMS PBMC (for virology/immunology studies)
- BLD/EDT/PLH or BLD/DPE/PLH aliquots (for SCA testing)
- LPK/SCI/CEL/DMS or LPK/ACD/CEL/DMS (Leukopak)
- LPK/SCI/LPK/RPM or LPK/ACD/LPK/RPM (Monogram)
- BLD/SCI/PL2 (D-dimer)
- BLD/DPE/PL1 (PK for raltegravir, dolutegravir, efavirenz)

NOTE: The completeness of the stored samples will be based on the LPC-required number of aliquots and a lower number (depending on the sample).

[ALIQ dataset, TXW0279 form]

7.9 Safety data

7.9.1 List of events

List showing all the grade > 0 safety events for each study participant. The list will include the following:

- public ID
- treatment dispensation days
- core team assigned code (regarding the relatedness to study treatment)
- visit week
- onset day
- resolution day
- event description
- value and units (for laboratory results)
- grade
- site assigned code (regarding the relatedness to study treatment)

NOTE: This information corresponds to the ToxSum report prepared by the DMC, with the addition of the site assigned code. The site assigned code is derived from the TRAC table for events, except for those who originate from the EVW0206; the site assigned code for these events is derived from the EVW0206_UPDATE dataset

[TRAC table, EVW0206_UPDATE dataset]

7.9.2 Dose escalation criteria (protocol Section 9.4.1, for dose escalation review only)

Criteria to be used to guide the SMC when determining dose resumption or dose escalation for each cohort are defined as:

 a) No more than three subjects have experienced a Grade 3 AE that is probably or possibly related to study treatment (as judged by the core team, blinded to treatment arm) prior to or on Day 14 after the treatment administration;

and

b) None of the subjects has experienced a Grade ≥ 3 AE that is definitely related to study treatment or that is Grade ≥ 4 and probably or possibly related to study treatment (as judged by the core team, blinded to treatment arm) prior to or on Day 14 after the treatment administration.

NOTE: The occurrence of a Grade 3 infusion site pain or tenderness that is sustained for less than 48 hours will be excluded from the dose escalation evaluation

7.9.3 Primary safety outcome (protocol Section 9.2.1.1)

List: Details of the following:

Occurrence of Grade \geq 3 AE including signs/symptoms, lab toxicities, and /or clinical events that is probably, possibly or definitely related to study treatment (as judged by the core team, blinded to treatment arm) any time from the time of study treatment administration until 28 days after the administration.

7.10 Cohorts 1-3 primary efficacy outcomes (protocol Section 9.2.1.2)

These analyses will be 'as-treated', such that only participants who completed study treatment/placebo administration will be included.

7.10.1 Change in plasma HIV-1 RNA levels from baseline (average of pre-entry and entry values) as detected by single copy assay (SCA) at 24 and 48 hours (average) after the administration of RMD or placebo.

The analysis of 7.10.1 will be combined with 7.11.1.

SCA values below the limit of detection (LOD) will be imputed as equal to half the limit of detection (i.e., if LOD=0.4 copies/mL, results < 0.4 copies/mL will be imputed as 0.2 copies/mL).

a. Tables:

- Completeness of data for all measurement time points
- N (%) of SCA value < LOD at all measurement time points
- Baseline SCA: N, median, 25th and 75th percentiles, min, max
- 24/48 hour SCA: N, median, 25th and 75th percentiles, min, max
- Change (24/48 hour baseline) SCA: N, median, 25th and 75th percentiles, min, max
- SCA at 6 and 12 hours, and 7, 14, and 28 days: N, median, 25th and 75th percentiles, min, max
- Change (at each above time point baseline) SCA: N, median, 25th and 75th percentiles, min, max

Note: Baseline and 24/48 hour averages will be calculated using log10-transformed SCA values.

A Wilcoxon rank sum test will be used for the comparison between groups.

b. Figure:

• Longitudinal, participant-specific, (spaghetti) plots for all measurement time points with open symbol for values below the LOD and different symbols/colors for RMD and placebo.

7.10.2 Change in cell-associated HIV-1 RNA levels in resting CD4+ T-cells from baseline to 24 hours after the administration of RMD or placebo.

The analysis of 7.10.2 will be combined with 7.11.2.

a. Tables:

- Completeness of data for all measurement time points •
- Baseline CA-RNA in resting CD4+ T-cells: N, median, 25th and 75th percentiles, min, max •
- 24 hour CA-RNA in resting CD4+ T-cells: N, median, 25th and 75th percentiles, min, max
- Day 14 CA-RNA in resting CD4+ T-cells: N, median, 25th and 75th percentiles, min, max •
- Change (24 hour baseline) of CA-RNA in resting CD4+ T-cells: N, median, 25th and 75th percentiles, min, • max
- Change (Day 14 baseline) of CA-RNA in resting CD4+ T-cells: N, median, 25th and 75th percentiles, min, • max

A Wilcoxon rank sum test will be used for the comparison between groups.

b. Figure:

Longitudinal, participant-specific, (spaghetti) plots for all measurement time points using different symbols/colors for RMD and placebo.

